14 POTENTIAL RISKS AND BENEFITS TO HUMAN SUBJECTS

There may be direct benefits to the participants in this study as they will experience a new lens fitting modality. Participation in this study may contribute to scientific research information that may be used in the development of new contact lens products.

This study is considered to be a non-significant risk study based on United States Food and Drug administration (FDA) and International Standards Organization (ISO) guidelines due to the daily wear nature of the study.

The lenses used in this study are approved by Health Canada and commercially available. The lenses are intended for daily wear (NOT extended wear). This study is a dispensing study. The participants' lens wear will be monitored closely by the investigators as participants will be able to be in close contact with the investigator by phone at any time.

Complications that may occur during the wearing of contact lenses include discomfort, dryness, aching or itching eyes, excessive tearing, discharge, hyperemia and variable or blurred vision. More serious risks may include photophobia, iritis, corneal edema or eye infection. Although contact lens-related infections are very infrequent with gas permeable rigid lenses, the possibility does exist. The occurrence rate of incurring a bacterial infection for patients that wear rigid gas permeable lenses is approximately two/10,000 per year. (11)

If the participant should experience any pain or discomfort during lens wear, any of the symptoms described above, or there is any health concern or a case of emergency, they are instructed to contact [name] or [name] at [contact] or [contact] [name], respectively.

Although participants with any known allergies or sensitivity to the diagnostic pharmaceuticals or products, drops such as fluorescein, used in this study would have been excluded, if any irritation occurs the participant will be instructed to contact the investigators.

14 UNINTENDED EVENTS

The imaging procedures outlined in this protocol will be carried out with instruments that are typically used in any optometric practice and therefore, there are no anticipated unintended events.

14 DISCONTINUATION FROM THE STUDY

Participants discontinued from a study will be compensated \$20 for each attended visit in the study. Participants will be discontinued at the discretion of the investigators or participant. The following is a list of possible reasons for discontinuation from the study:

- Screening failure: Participants will be discontinued if they do not meet the inclusion and exclusion criteria outlined in section 4.2.2.
- Positive slit lamp finding: Participants may be permanently discontinued from the study depending on the severity of the condition and on the judgement of the investigator.
- Unexpected adverse event: If a participant experiences an adverse event (excessive redness or dryness), at the discretion of the investigator, the participant may be excluded from the study.
- Symptoms: If the participant has persistent symptoms (excessive redness or dryness), the participant may be discontinued from the study based on the clinical judgement of the investigator.
- Disinterest, relocation or illness: The participant may choose to discontinue due to reasons within or beyond their control.
- Violation of protocol or non-compliance: The participant will be discontinued if they are unable or unwilling to follow the protocol specified visit schedules and/or study procedures.
- Lost to follow-up: The participant will be discontinued if they cannot be contacted and does not return for a final exit visit, and if the investigator has made a reasonable effort to contact the participant for a final study visit.
- Premature termination of the study by the Office of Research Ethics at the University of Waterloo.

14 STUDY COMPLETION AND REMUNERATION

Once their involvement in the study is complete, participants will be informed about receiving feedback following study completion in the Letter of Appreciation (Appendix 6).

Participant remuneration will be up to \$120 for completing the study and is typically paid at the end of the study (Appendix 7).

14 STATISTICAL ANALYSIS AND DATA MANAGEMENT

13.1 STATISTICAL ANALYSIS

All data described above will be analysed at the University of Waterloo from the eye(s) wearing the semi-scleral contact lens(es). Data analysis will be conducted using Statistica 12. Descriptive statistics will be provided on information regarding baseline variables (age, gender, sagittal depth distribution, etc.). Table 3 lists the primary outcome variables and anticipated statistical procedures.

Table 3: Statistical procedures

Variable	Analysis	Statistical test
Parametric (tear clearance, NIBUT, comfort ratings, tear components)	Comparison of lens 1 to lens 2	ANOVA Paired t-test

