14 PURPOSE AND HYPOTHESIS

The purpose of this study is to investigate changes in the level of inflammatory mediators in the tear film of scleral contact lenses wearers. The hypothesis is that scleral contact lens wear is associated with inflammation in the tear film. Furthermore, the level of proteases and cytokines will be altered in samples collected post scleral lens wear compared to those collected pre-lens wear. Additionally, the amount of alteration will correlate to the fitting characteristics in the limbal zone of the scleral lenses.

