14 MATERIALS AND METHODS

13.1 STUDY DESIGN

12.1.1 OVERALL DESIGN

This will be a prospective cross-over, dispensing study design. The study will involve up to 20 keratoconic participants.

Participants will attend 1 screening/fitting visit wearing their habitual contact lenses where the two test lens designs will be fitted. There then will be a dispensing visit for each design (randomly selected) and a single follow up visit 2 weeks later after 6-8 hours of scleral lens wear. A washout period of a minimum of 72 hours will be applied between the cross-over of each lens design.

Lenses to be worn in this study will be made of Boston XO material and are approved by Health Canada. The lenses will have a diameter of 14.8 to 17.8mm with a high and low sagittal depth at the limbal zone. As to which of the two lenses is being assessed, both the investigator and the participant will be masked.

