13.2 STUDY POPULATION

12.2.1 SAMPLE SIZE CALCULATION

A sample of 15-20 participants was chosen according to historical data on tear assessment in this group of participants.

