12.3.5 TEAR FILM ANALYSIS

Tear film analysis is performed using antigen capture enzyme linked immunosorbent assay (ELISA). (5) After collection, the tear samples are stored at -80°C until analysis. Preparation of the samples includes dilution with phosphate buffered saline (PBS) containing 1% (w/v) bovine serum albumin and incubation with specific antigen. The tears are assayed for specific proteinase and cytokines using commercially available ELISA kits. Preparation and analysis of samples are as per instructions supplied by manufacturers.

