12.4.2 STUDY VISITS

This study will involve 6 visits over 5 study days. The total time commitment for all study visits is approximately 6 hours. The total study visit time commitment may be different for each participant, as the needed visit time will depend on how easily the lenses can be fitted.

The first visit will involve screening of the participants and baseline measurements. The investigator will determine the eligibility of the participant using the inclusion/ exclusion criteria. Ineligible participants will be discontinued from the study. The investigator will also perform baseline tear collection.

At the lens fitting appointment, the participants will be fitted with the scleral contact lenses based on the baseline measurement obtained at the screening appointment. Participants will be instructed on insertion, removal, and proper handling of the lenses.

At each of the lens delivery appointments, the researcher will deliver the study lenses. Measurements, including bulbar hyperemia and pre-lens NITBUT, will be obtained while the participants are wearing the lenses.

After the participant has worn the lenses during the day for two weeks, the participant will return for a follow up visit. At each of the follow up appointments, the lens fit and measurements, including bulbar hyperemia and pre-lens NITBUT, will be repeated while the participants are wearing the lenses. Tear samples will be collected from the study lenses after lens removal.

A wash-out period of minimum of 72 hours is required between the first follow up visit and the second lens delivery visit.

Table 1 provides a summary of the study visits.

Table 1: Summary of visits

Visit code	Visits	Time
0-0	Screening and baseline measurements	1hr±½ hr
1-1	Lens fitting	1hr±½ hr
2-1	Lens Delivery visit - Lens 1	1hr±½ hr
2-2	Follow-up visit - Lens 1	1hr±½ hr
3-1	Lens Delivery visit - Lens 2	1hr±½ hr
3-2	Follow-up visit - Lens 2	1hr±½ hr

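### Does Table 3 need a stated scale, an undetectable-value rule and a fallback test for the ELISA tear components?

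*Combined protocol and SAP*

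**What the plan says.** The Purpose and Hypothesis section expects that "the level of proteases and cytokines will be altered" after lens wear, so the tear measurements carry the hypothesis. Section 12.3.5 says "The tears are assayed for specific proteinase and cytokines using commercially available ELISA kits" and leaves preparation and analysis to the kit instructions. It also describes a dilution step: "Preparation of the samples includes dilution with phosphate buffered saline (PBS". Section 12.4.2 adds "Tear samples will be collected from the study lenses after lens removal".

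On the analysis, section 13.1 states "Table 3 lists the primary outcome variables and anticipated statistical procedures". The table's one row begins "Parametric (tear clearance, NIBUT, comfort ratings, tear components" and gives lens 1 against lens 2, by ANOVA or paired t-test. No section mentions a transformation, a check of distribution, a detection limit or a rank test.

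On size, section 12.2.1 says only "A sample of 15-20 participants was chosen according to historical data on tear assessment in this group of participants". It gives no standard deviation, effect, alpha or power. Section 12.1.1 says of the lens assignment that "both the investigator and the participant will be masked".

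**The concern.** Tear proteases and cytokines share a row with comfort ratings and break-up time, as if all four behaved alike. Concentrations cannot be negative. Errors in recovered volume or dilution multiply the result, so variation that grows with the level is plausible. In that case a t-test on untransformed differences is driven by the few participants with high levels. With 15 to 20 pairs, that could hide a real lens difference.

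Two further worries follow. An analyst who treats the scale as open could try several tests and report the best one. Values below the assay limit have to be given some number, and on a log scale that number can matter a good deal. At stake are the power and interpretation of the study's central comparison.

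**Working it through.** **Inputs.** From the documents: a two-lens cross-over, 15 to 20 participants, and a paired comparison of lens 1 with lens 2. Not in the documents, and so assumed: two-sided alpha 0.05, 80% power for the reference test, total CV (between plus within person) of a single measurement of 31% or 131%, and within-person correlation 0.3 to 0.8. The plan gives no power figure to reproduce.

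**Step 1, conversion.** For log-normal data, log-SD = sqrt(ln(1 + CV²)).
- CV 0.31: sqrt(ln 1.0961) = 0.303.
- CV 1.31: sqrt(ln 2.7161) = 1.00.

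**Step 2, effect.** From the noncentral t, a paired t-test has 80% power at a standardised difference of 0.778 (n = 15) or 0.660 (n = 20). On the log scale the shift is that value × log-SD × sqrt(2(1 − correlation)). For example, with n = 15, log-SD 1.00 and correlation 0.5, the shift is 0.778 × 1.00 × 1 = 0.778, a ratio of exp(0.778) = 2.18.

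**Step 3, proportional variation.** Simulated power lost by the untransformed paired t-test when the log test has 80%:

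| Total CV | n = 15 | n = 20 |
|---|---|---|
| 31% | 2.2 to 2.9 points | 2.3 to 3.0 points |
| 131% | 24.6 to 30.1 points | 23.3 to 29.2 points |

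With no lens effect, the untransformed test rejects about 5% of the time at log-SD 0.3 and 3 to 4% at 1.0. The possible harm is lost power, not false positives.

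**Step 4, additive within-person noise.** Person levels are log-normal, the noise is normal, the lens effect is a constant shift, and the untransformed test is set at 80%. Log-test power is then about 74 to 77% at CV 31% (loss 80 − 77 = 3 to 80 − 74 = 6 points) and 48 to 53% at CV 131% (loss 27 to 32). The direction reverses and the size is similar.

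**Step 5, fixed effects.** Under proportional variation with between- and within-person log-SD of 0.5 and 0.4, untransformed against log power is:
- 1.5-fold effect: 61% against 73% (n = 15), and 75% against 86% (n = 20).
- 2-fold effect: 96% against 99%, and 99% against 100%.

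**Step 6, undetectable values.** Suppose 10% of lens 1 samples fall below the limit, with correlation 0.6 and log-SD 0.5 to 1.0.
- The log test goes from 80% to 77 to 79% with half the limit substituted, to 70 to 71% if those pairs are dropped, and to about 43 to 66% with a hundredth of the limit.
- The untransformed test moves by about 2 points or less: in one setting, 72.7% becomes 73.5% with half the limit and 74.4% with a hundredth of it.

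**Step 7, choosing after the data.** Under the proportional null, taking the smaller p-value of the untransformed and log tests gives a type I error of 5.5 to 7.0%. Adding the signed-rank test gives 6.1 to 7.9%, an excess of at most 7.9 − 5 = 2.9 points.

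**The case for a change.** The strongest case for a change is that the gap is real and cheap to close. Tear components are among the primary outcome variables, their procedures are only anticipated, and one line fixing the scale and the detection-limit rule would cost nothing but wording. Proportional variation is also the more plausible model, given dilution and collection from the lens. The signed-rank test limits the damage: at log-SD 1.0 it loses 8 to 11 points, against 23 to 30 for the untransformed t-test.

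Much of this stands. The plan is silent, the conditional figures are correct, and a fixed scale is better practice than an open one. It does not show that the plan as written is worse than the alternative:
- The preference for logs is an inference, and if it is wrong a log default loses about as much as it was meant to save.
- A paired t-test on logs is itself parametric, so the label leaves room for it.
- The large effect of the detection-limit rule belongs mainly to the log analysis. The untransformed test, which is the plain reading of Table 3, hardly depends on it, and nothing in the documents says undetectable values are expected.
- Fixing the choice before unmasking would not prevent selection. A two-sided paired p-value is the same when the lens labels are swapped, so a masked analyst could still pick the smallest.
- A signed-rank fallback with no rule for when it takes over would itself allow the best-of-three choice.

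**Conclusion.** No change to the plan is called for. The omission is real, but it is detail that an analyst can settle sensibly by looking at how the spread of within-person differences behaves, together with a fair trade-off between scales. Depending on an unknown variance structure, the untransformed test is behind by about 2 to 3 points (CV 31%) to 23 to 30 points (CV 131%), or ahead by about 3 to 6 to 27 to 32 points. Any one scale fixed in advance keeps type I error at or below about 5%. Deliberate selection among three tests would raise it to at most about 8%.

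These figures rest on assumed spreads, on n = 15 to 20, and on CV meaning the total for one measurement. If 31% were the within-person CV alone, the proportional loss would be about 5 to 33 points, depending on between-person spread. They also assume one value per participant per lens and no period term. Only then does a two-lens ANOVA with participant as block reproduce the paired t-test (F = t²); section 13.1 allows one or both eyes.

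The conclusion would change if the historical tear data behind section 12.2.1 included repeat measurements showing clearly that within-person differences grow with the level. The documents report no such data. The Clinical Trial Registration section describes early feasibility work, so a general parametric label with anticipated tests is adequate here.

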13.5 STUDY PROCEDURES

12.5.1 SCREENING, BASELINE AND EXPERIMENTAL MEASUREMENTS

Screening & Baseline procedure: Participants will present to the screening visit. Their corneal sagittal depth which will be measured with the Visante OCT, auto-refraction and associated visual acuity measurements and corneal topography carried out and biomicroscopy performed, along with hyperemia imaging and pre-lens non-invasive tear break up time. Eligibility will be confirmed and a baseline biomicroscopy assessment will be performed. (Visit 0-0)

Bulbar and Limbal Redness assessment: The eyes of the participants will be imaged using the Keratograph® 4. Participants will be asked to be seated at the Keratograph 4 instrument and will be asked to blink 2-3 times and hold their eye open for a few seconds until the instrument software takes a picture of the eye. This image will be repeated three times.

Flush tear collection method: This procedure entails the instillation of a small amount non-preserved saline, 60 μ L, into the inferior palpebral fold. After which, the fluid can be collected with a micro-capillary tube. (9,10) All samples are collected by the researcher. (Visit 0-0)

Fitting of the semi-scleral lenses: Participants will be fitted each of the two sets of semi-scleral lenses of varying sagittal depth at the limbal zones. Fittings will be done using the corneal sagittal depth which was measured at the screening/baseline visit with the Visante OCT. The lenses will be made of the same gas permeable lens material Boston XO. The lens fit will be evaluated; over-refraction and visual acuity determined. Participants will be instructed on insertion, removal, and proper handling of lenses. (Visits 1-1)

Video Imaging procedure with test lenses: The lens fitting will be imaged using a video-slit lamp and the Visante OCT after the lens delivery appointment (Visits 2-1 & 3-1) and at the follow up appointment. (Visits 2-2 & 3-2)

Pre-lens Non-invasive tear break up time (NITBUT) with test lenses: Pre-lens NIBUT will be measured with the study lens after lens delivery (Visits 2-1 & 3-1) as well as at the follow up visits (Visits 2-2 & 3-2). Participants will be asked to be seated at the Keratograph 4 instrument and will be asked to blink 2-3 times and hold their eye open for a few seconds until the instrument software takes a measurement of the NITBUT. This measurement will be repeated three times.

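### Table 3 plans a paired t-test or an unspecified ANOVA for a crossover whose lens order is randomised but not balanced; a period-adjusted analysis with blocked orders would be a cheap improvement

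*Combined protocol and SAP*

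**What the plan says.** Section 12.1.1 (Overall design) describes a crossover of two lenses that differ in sagittal depth at the limbus. On order it says: "There then will be a dispensing visit for each design (randomly selected) and a single follow up visit 2 weeks later". It gives no ratio, block size or rule for equal numbers in the two orders, and neither does any other section.

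The analysis plan is the short section 13.1 (Statistical analysis). It states that "Table 3 lists the primary outcome variables and anticipated statistical procedures". The single row of Table 3 has the analysis "Comparison of lens 1 to lens 2" and the test "ANOVA Paired t-test". Period, sequence and participant are not named. The section takes data from one or both eyes of each participant.

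On exposure before each period, section 12.1.1 says "Participants will attend 1 screening/fitting visit wearing their habitual contact lenses", and no washout is stated before the first study lens. Section 12.4.2 (Study visits) says "After the participant has worn the lenses during the day for two weeks, the participant will return for a follow up visit", and then: "A wash-out period of minimum of 72 hours is required between the first follow up visit and the second lens delivery visit".

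**The concern.** In a two-period crossover, anything that changes between the first and second period enters each participant's lens difference, with a sign that depends on the order received. A paired t-test treats that as noise. If the orders are unequal, part of it also moves the estimate.

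A period effect is plausible here. The first period follows habitual lens wear. The second follows two weeks in the other study lens and a washout of at least 72 hours. Comfort ratings, one of the Table 3 outcomes, may also change as participants get used to the lenses.

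The lens comparison is the only analysis in Table 3, and with 15-20 participants there is little power to spare. An ANOVA could carry a period term, but the model is not written down and the procedures are only anticipated, so the choice stays open until data are in hand.

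**Working it through.** **The plan's own figure.** The 15-20 participants (section 12.2.1) cannot be reproduced: no significance level, power, effect or SD is given. All values below are assumptions that show scale.

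**Assumptions.** Two-sided 5%; one high-minus-low difference per participant; SD of that difference = 1; true design effect d = 0.66, which gives a paired t-test about 80% power at n = 20 (at n = 15 the corresponding effect is 0.78). The period effect p (period 2 minus period 1) is 0.1, 0.25, 0.5 or 1 SD. n1 participants wear the high lens first and n2 the low lens first; n = n1 + n2.

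**Unadjusted paired t-test.**
- Expected mean difference: d - p(n1-n2)/n.
- Expected variance of the observed differences: 1 + 4·n1·n2·p²/[n(n-1)].
- At 10:10 and p = 0.5: 1 + 4·100·0.25/(20·19) = 1 + 5/19 = 1.26. At p = 1: 1 + 20/19 = 2.05.
- Power comes from integrating over a normal mean and a noncentral chi-square residual sum of squares. At unequal splits it is the mean of both directions.

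**Period-adjusted test.** The estimate is half the sum of the two sequence means, SE = 0.5·√(1/n1 + 1/n2), with n-2 df, and does not depend on p. At 10:10 the SE is 0.2236, the noncentrality is 0.66/0.2236 = 2.95 on 18 df, and power is 79.7%.

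**Power.**

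| Split | p = 0 | 0.1 | 0.25 | 0.5 | 1 | With period term |
|---|---|---|---|---|---|---|
| 10:10 | 79.9% | 79.6% | 78.1% | 72.2% | 49.4% | 79.7% |
| 8:7 | 66.2% | 65.8% | 63.8% | 56.7% | 33.6% | 65.5% |

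At 10:10 the term pays for itself once p exceeds about 0.09 SD.

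**Shift in the unadjusted estimate.** (12-8)/20 = 0.2, (13-7)/20 = 0.3 and (14-6)/20 = 0.4 times p. At 14:6 with p = 0.5 that is 0.20 SD, and 0.20/0.66 = 30% of the assumed design effect.

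**Type I error without the term, given the split.**

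| Split | p = 0.1 | 0.25 | 0.5 | 1 |
|---|---|---|---|---|
| 10:10 | 4.9% | 4.4% | 2.9% | 0.6% |
| 12:8 | 5.0% | 4.9% | 4.5% | 3.0% |
| 13:7 | 5.1% | 5.5% | 6.6% | 7.5% |
| 14:6 | 5.2% | 6.4% | 9.7% | 16.5% |

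Averaged over simple randomisation, simulation gives about 5.0% at n = 15 and n = 20 for p = 0, 0.5 and 1.

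**How often the orders are uneven.** From Binomial(20, 0.5): 12:8 or closer in 74% of trials, 13:7 or worse in 26.3%, 14:6 or worse in 11.5%.

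**Price of the term when p = 0.** 79.9% falls to 75.9% at 13:7 (4.0 points) and to 72.5% at 14:6 (7.4 points). Averaged over simple randomisation of 20, adjusted power is 77.5%, so without blocking the term breaks even only at p of about 0.25 SD.

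**Both eyes.** If both eyes enter a model whose only random term is participant, lens is tested against variation between eyes. With correlations of 0.3 to 0.8 between a participant's two eyes in the lens difference, type I error is roughly 8% to 15%.

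**The case against.** The strongest reply is that every loss depends on a period effect that the documents do not show. At 0.1 SD and 10:10 the loss is 0.1 point, and at 0.25 SD it is 79.7 - 78.1 = 1.6 points. The striking figures need 1 SD, which is larger than the assumed design effect. That stands, and it limits the weight of the point.

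Tear components are sampled at follow-up, after two weeks in the study lens, so the habitual lens may have little influence left. That also has force. What remains from the first study lens is carry-over: if it is equal in both orders it acts like a period effect, and if it is unequal a period term does not remove it.

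Adjustment does not always gain. At n = 15 under simple randomisation, mean adjusted power is 62.6% against 66.2% unadjusted with no period effect, with break-even near 0.30 SD. This is why the term and blocking belong together.

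This is also an early feasibility study for a thesis, not meant for regulatory use. That lowers the stakes, but writing down the model is still nearly free.

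Three stronger readings are tempting. A reader might infer that the ANOVA has no factors at all; the analysis column implies lens, and what is missing is the rest of the model. A reader might infer that false positives are generally inflated; the average rate stays near 5%, and the test is conservative at 12:8 or closer. A reader might infer from Table 1, where Lens 1 and Lens 2 mark dispensing order, that Table 3 compares first with second period. The purpose, the objectives and section 12.5.1 point to limbal depth as the contrast: "Participants will be fitted each of the two sets of semi-scleral lenses of varying sagittal depth at the limbal zones". The labels need defining, but the documents do not support reading the planned contrast as one of order.

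**Conclusion.** The point holds as a cheap improvement. The plan randomises lens order without balancing it, names a test that cannot carry a period term, and leaves the ANOVA model beyond lens unstated. If a period effect exists, the harm is lost power (79.7% to 72.2% at 0.5 SD, n = 20, 10:10) and, in an unevenly split trial, a shifted estimate. If none exists, the planned paired test is sound and slightly more powerful. The sizes rest on assumed values for the design effect, the period effect and the significance level, and on one difference per participant.

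**What to change.** Adopt both changes together.

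1. In Table 3, replace the named tests with a period-adjusted two-period, two-sequence crossover analysis. Define the contrast as the high- versus low-limbal-depth lens, identified from the randomisation code and not from dispensing order. Use one value per participant per period (the study eye, or the mean of both eyes), with lens, period and sequence fixed and participant random; the two-sequence t-test is equivalent. If eyes are modelled separately, add random terms for eye and for participant-by-lens, so that lens is tested at participant level.
2. In section 12.1.1, allocate the two orders in permuted blocks. Blocks of 4, for example, keep the enrolled numbers within 2 of each other.

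The cost is some wording, a blocked list and one degree of freedom. With no period effect and near-equal orders the power cost is 79.9 - 79.7 = 0.2 points at 10:10 and 66.2 - 65.5 = 0.7 points at 8:7.

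Blocking does not protect against dropout. If 5 of 20 leave at random from 10:10, completers are 9:6 or worse in 30% of trials. Mean adjusted power is then 64.9%, against 66.2% unadjusted with no period effect and 63.7%, 56.7% and 34.9% unadjusted at 0.25, 0.5 and 1 SD. No extra participants, visits or measurements are needed.
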